Project Title:

LIDOCAINE IN THE TREATMENT OF POST-OPERATIVE PAIN
MANAGEMENT FROM A DONOR SITE AFTER SPLIT THICKNES SKIN GRAFT
HARVESTING FOLLOWING BURN INJURY OR WOUND TREATMENTS

NCT #:

NCT02229578

Document date:

December 08, 2016

Protocol

1. Project Title:

LIDOCAINE IN THE TREATMENT OF POST-OPERATIVE PAIN MANAGEMENT FROM A DONOR SITE AFTER SPLIT THICKNESS SKIN GRAFT HARVESTING FOLLOWING BURN INJURY OR WOUND TREATMENTS

2. Investigator(s): **[name]**

[name]

[name]

[name], ARNP

[name]

3. Abstract:

Burn pain is known to be one the most severe forms of acute pain often requiring large amounts of narcotics in addition to other adjuvants. Wounds can also cause a great deal of pain in this population. Topical lidocaine is effective for controlling pain in various settings including dressing changes of burns. The aim of this study is to demonstrate the effectiveness of topical lidocaine in decreasing pain scores and narcotic requirements when applied to donor graft sites while at the same time not interfering with the standard of care TheraBond dressing. During this study we will be monitoring for evidence of delayed wound healing, and surgical site infection.

4. Background:

Pain from burns is a severe form of acute pain that requires aggressive use of opioids.¹ Even with the implementation of multiple modalities for analgesia, pain from skin debridements and grafting procedures remains a challenge to control.^{2,3} Local anesthetics have been used for pain relief in burn patients previously as a topical gel or IV infusion and have been found to significantly reduce medication consumption, without apparent adverse effects on wound healing.^{2,4,5} Lidocaine actually has potent anti-inflammatory effects which could be advantageous on wounds.¹ In addition, topical application of lidocaine to wounds result in different degrees of systemic absorption. High concentrations of lidocaine have potential for central nervous system (seizures ($>5\text{mg/L}$)) and cardiovascular toxicity (arrhythmias ($>9\text{mg/L}$)).⁴ Plasma concentration of lidocaine depend upon drug dose, rate of absorption, patient weight, physical status and thickness of skin harvested.⁶ A prior study where up to 6.7mg/kg of 2% lidocaine with epinephrine was sprayed on donor

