graft sites found that systemic lidocaine levels were far below toxic levels at their peak (average level of 1.4, with maximum level at 2.2). In this study the levels peaked between 30 and 60 minutes and systemic levels of lidocaine were detectable 6 hours following application of the solution.² Studies have demonstrated the beneficial effects of systemic lidocaine administered via IV infusions in reducing perioperative pain scores.^{7, 8} Topical lidocaine is effective as a topical anesthetic in multiple clinical trials however only two studies to date has shown that topical lidocaine applied to skin-harvest sites produces an analgesic effect, reduces narcotic requirements while not affecting wound healing or causing toxic blood concentrations. In both these studies systemic intravenous lidocaine levels were monitored and were found to be significantly below toxic limits.^{2,9} The use of topical lidocaine on donor sites is still not widely used, partly for fear the lidocaine will interfere with wound healing and/or dressing adherence. No study to date has demonstrated lidocaine solution to be effective on burn sites when used in conjunction with TheraBond silver foam dressing. TheraBond is an absorbent, atraumatic dressing coated with ionic silver that is routinely used on donor sites at our institution. This study will also offer additional supporting evidence that topical lidocaine is effective in post-operative pain management of donor skin sites and should be more widely utilized. In addition, this study will serve as a stepping stone for analyzing different local anesthetic solutions in the future and the potential for reapplication to surgical sites.

5. Specific Aims:

The purpose of this study is to offer the medical community data on a simple and relatively cheap adjuvant that can be utilized to help reduce the amount of post-operative pain and narcotic requirement in burn and wound patients requiring skin grafts.

6. Research Plan:

Study Design

- a) Randomized Controlled Double-Blind Study
- b) Burn and wound patients undergoing general anesthesia for split thickness skin graft with a 1-15% TBSA donor site who will be treated at UF Health Shands Hospital

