- c) Consent will be obtained from non-intubated patients willing to participate in the study that are admitted to the Burn Service for treatment of their burn or wound. All patients will undergo general anesthesia. Standard induction will be performed with Fentanyl and Propofol. Maintenance will primarily be with the volatile agent sevoflurane. Acetaminophen 1g IV and Ketorolac 30mg IV will be administered for baseline pain control intraoperative within the last 30 minutes prior to extubation. Fentanyl, Hydromorphone or Morphine will be

titrated in at end of the case as part of standard management. Hydromorphone, as needed (PRN), orders will be written for pain control in the recovery room as well as one time dose of Oxycodone 5-15mg PO. If patient requires more than 2mg of Hydromorphone then subsequent pain will be treated with Ketamine IV (10mg every 15 minutes up to 50mg total) and 1-2mg of IV midazolam. If pain is still not adequately controlled patient will be treated with an additional 2mg of Hydromorphone IV and Hydromorphone PCA will be initiated. Once discharged from the PACU to the surgical floor the patient will have PRN Oxycodone PO every 4 hours and/or Hydromorphone PO every 4 hours in addition to PRN Hydromorphone 0.2-0.5mg available. If pain control is still not adequate patient will be started on Hydromorphone PCA. The amount of hydromorphone required in PACU and in the first 24 hours following surgery will be compared between the two groups as well as self-reported donor site and overall pain according to the Verbal Numerical Rating Scale (VNRS) obtained from the patient by Research staff and by the hospital staff per standard of care.

- d) Lidocaine 2% with Epinephrine 10 μ g/mL will be placed on the donor site immediately following harvesting until hemostasis has been obtained per the surgeon. The total of up to 7mg/kg, as recommended by leading anesthesia textbooks, of lidocaine solution will also be sprayed onto the patient's donor site based on patient's ideal weight (BMI 25 or actual patient's weight if BMI <25).¹⁰
- e) 50 patients split into two (study & control) groups.

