- c. All patients enrolled in the study will have risks and benefits thoroughly explained to them.
- d. Any adverse events will be well documented and thoroughly investigated. Seriousness of event will be assessed by the Principal Investigator. All events deemed serious will be submitted to the University of Florida Institutional Review Board in accordance with institutional policy.
- e. Dressing site will be evaluated daily per standard of care by the burn team until hospital discharge.
- f. After 10 additional evaluable patients, have been enrolled a second safety analysis will be performed; all investigators will be involved in data interpretation.

Analysis Plan

An independent groups t-test (Student's t-test) will be performed to compare the mean rating between the difference of the two reported pain scale ratings. Each patient will be used as his/her own control by comparing the amount of narcotics utilized prior to surgery. An alpha level of 0.05 and power of 0.8 will be used to address the difference in the two groups. Given the desired alpha the sample size was estimated by pre-determined tables for certain values, by Mead's resource equation. With an effect size (Cohen's d) of 0.8 it is estimated that 25 patients in each

group will be needed in order to show statistical significance. An interim analysis will be conducted at 10 patients in each group and significance will be analyzed.

The amount of hydromorphone utilized in the PACU immediately post op and within the first 24 hours will be compared between the two groups and trended within the same group. Once again, an independent groups t-test will be performed to compare the mean quantity of hydromorphone required between the two groups. An alpha level of 0.05 and power of 0.8 will be used to address the difference in the two groups.

7. Possible Discomforts and Risks:

The patient's regular medical care will not change because they are enrolled in this study.

Possible risks to you may include:

- The risks from skin grafting and donor site include those associated with any surgical procedure that involves general anesthesia. These include reactions to the anesthesia, medications, nausea, pain, problems breathing, excessive bleeding, and infection.

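### The only narcotic comparison with a named test counts hydromorphone alone, although oxycodone is ordered in the same windows; no total-opioid measure, common unit or order of priority is defined

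*Combined protocol and SAP*

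**What the plan says.** **The aim.** The Abstract sets out to show that topical lidocaine is effective in "decreasing pain scores and narcotic requirements when applied to donor graft sites". Specific Aims speaks of an adjuvant to "help reduce the amount of post-operative pain and narcotic requirement in burn and wound patients". Neither restricts the outcome to one opioid.

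**The measure that is tested.** Section 6, Study Design item c: "The amount of hydromorphone required in PACU and in the first 24 hours following surgery will be compared between the two groups". The Analysis Plan repeats this measure and assigns it an independent-groups t-test, to "compare the mean quantity of hydromorphone required between the two groups".

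**What patients may receive in those windows.** All of this is in Study Design item c.
- In PACU, as-needed hydromorphone is ordered "as well as one time dose of Oxycodone 5-15mg PO". If pain persists after the intermediate steps, an "additional 2mg of Hydromorphone IV and Hydromorphone PCA will be initiated".
- On the floor, "the patient will have PRN Oxycodone PO every 4 hours and/or Hydromorphone PO every 4 hours", "in addition to PRN Hydromorphone 0.2-0.5mg available". A hydromorphone PCA may follow.

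**Other narcotic analyses.**
- Study Design item f compares narcotic medication between groups, and scales it by ideal weight, actual weight and donor area.
- The Study Intervention text for Groups A and B adds an analysis of how fast the narcotic requirement rises over the first 24 hours.
- The Analysis Plan mentions narcotics used before surgery as each patient's own control.

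None of the three is given a test or a common opioid unit.

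**Data.** The Study Table of Events schedules narcotic data collection from surgery to 48 hours. Appendix A lists overall narcotic data to 72 hours after surgery. Appendix C says only that medication data go into a spreadsheet.

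**The concern.** The trial asks whether lidocaine lowers narcotic requirement, and the one test specified for that counts one of two opioids ordered in the same windows. On the floor, oral oxycodone and oral hydromorphone can stand in for each other, so two patients with equal opioid need can score differently because different drugs were chosen. A difference in mean hydromorphone could then reflect drug or route mix, and a real reduction could be partly hidden if it fell on oxycodone.

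The plan also contains a broader comparison (item f) that could answer the aim. It cannot be computed as written, because milligrams of different opioids have to be put on one scale first and no scale is given. Nor does the plan say which result prevails if the hydromorphone and all-narcotic comparisons disagree. Those choices would be left until after data are available, and the Analysis Plan schedules a significance look at 10 patients per group.

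**Working it through.** **1. The plan's own figure.** The Analysis Plan gives 25 per group for Cohen's d = 0.8, alpha 0.05 and power 0.8. Two-sided normal approximation: n = 2(1.960 + 0.842)² / 0.8² = 24.5, so 25. The exact t calculation gives 25.5, so 26, with power 0.79 at 25. The stated size reproduces. The d of 0.8 appears in the pain-rating paragraph; the hydromorphone paragraph repeats alpha and power but gives no effect size, mean or SD.

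**2. Drugs ordered against drugs counted.**
- PACU: hydromorphone ordered and counted; oxycodone (one oral dose) ordered, not counted.
- Floor, within 24 hours: hydromorphone (oral, as-needed small doses with no route stated, PCA) ordered and counted; oxycodone (oral, as needed) ordered, not counted.
- Oral hydromorphone first appears after PACU discharge. The missing route rule therefore matters for the 24-hour total; in PACU the gap is mainly oxycodone.

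**3. What the score does.** Let H be hydromorphone, X oxycodone and c the oxycodone milligrams equal to 1 mg of hydromorphone. Total use is T = H + X/c; the named test uses H. A patient who takes all of T as hydromorphone scores T, and one who takes half of it as oxycodone scores T/2. Their requirement is the same, whatever c is.

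For route, suppose k oral mg equal 1 mg IV (k assumed; the documents give none). A recorded 4 mg taken orally is worth 4/k IV-equivalent: 4.0, 2.0, 1.33 and 0.8 mg for k = 1, 2, 3 and 5. This matters only if oral and parenteral milligrams are added as they stand, which the plan neither states nor excludes.

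**4. Type I error.** I simulated 40,000 trials with 25 per group, two-sided t-test at 0.05, equal mean total use in both arms and a hydromorphone share drawn uniformly from 0 to 1 regardless of arm. Rejection rates are about 0.05 for total opioid and about 0.05 for hydromorphone alone.

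**5. Power, to see whether a direction can be claimed.** All inputs are assumptions in an arbitrary common opioid unit, with values clipped at zero.
- (a) Lidocaine lowers total use, mean 6 against 4, SD 2.5, so d = 2/2.5 = 0.8. Power is 0.79 for the total. For hydromorphone alone it is 0.74 if its share averages 0.8 (Beta(8,2)), 0.63 if it averages 0.5 (Beta(5,5)) and 0.38 if it is uniform on 0 to 1.
- (b) Lidocaine lowers hydromorphone only, 6 against 4, SD 2.5, with independent oxycodone of mean 3 in both arms. Power is 0.78 for hydromorphone. For the total it is 0.72 (oxycodone SD s = 1) or 0.66 (s = 1.5).
- (c) Break-even. With independent components, the total has d = (2 + δ)/√(2.5² + s²), where δ is the fall in oxycodone. It matches 0.8 when δ = 0.8√(6.25 + s²) − 2, which is 0.15 for s = 1 and 0.33 for s = 1.5, against a fall of 2 in hydromorphone. Above that the total has more power; below it, less.
- (d) A PACU-like case: total 3 against 2, SD 1.25, of which a one-time oxycodone amount unrelated to arm (uniform on 0.25–0.75, 0.5–1.5 or 0–1.5) goes uncounted. Hydromorphone alone has power 0.74 to 0.78, against 0.79 for the total.

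The sign of the effect changes between (a) and (b), and the documents do not say which is closer.

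**The case against.** The choice of hydromorphone looks deliberate. It is named as the comparison in both Study Design item c and the Analysis Plan, it is the drug carried through the escalation steps, and allergy to it is an exclusion. It is also a real part of narcotic requirement, so a reader who inferred that the test fails to measure the outcome at all would go too far: it measures it incompletely. Nor does the plan ignore oxycodone, since item f commits to an all-narcotic comparison. These points stand. They do not supply the missing unit, test or priority, and no document gives hydromorphone's share of opioid use.

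A reader might also infer that oral and IV milligrams will be summed. No section says so; the supportable statement is that no route rule is given for the 24-hour window.

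The power figures can be challenged too. The lowest, 0.38, needs a uniform drug share, which does not suit PACU, where oxycodone is a single limited dose; case (d) shows little loss there. In case (b) the total measure is the weaker one. The figures therefore bound nothing.

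**Conclusion.** The concern holds as a matter of what is measured. The only narcotic test specified covers part of the stated outcome and depends partly on drug choice; the broader analyses lack a common unit, a test and a rank. This rests on the text alone and needs no assumption about opioid use.

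Two stronger conclusions are not supported. One is an inflated false-positive rate: if drug choice is unrelated to arm, type I error stays at about 5%. The other is that the trial is underpowered because of this choice. The documents give no opioid means, SDs, drug shares or conversion factors, so neither the size nor the direction of any power effect is known.

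The practical consequence is that a hydromorphone result alone would not support a claim about narcotic requirement. It should be fixed before efficacy data are compared by arm.

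**What to change.** In the Analysis Plan:
- Make the named narcotic test total postoperative opioid (all hydromorphone by route, oxycodone and any other postoperative opioid) in PACU and over 0–24 hours, in one opioid-equivalent unit.
- Fix the conversion table before any unblinded efficacy comparison, including the interim at 10 per group.
- State that opioids titrated at the end of surgery lie outside this total and are reported by arm.
- Use the same unit in Study Design item f and for the rate of increase in the Study Intervention text, and bring Study Design item c into line.
- Designate one version as the main test, for example the unscaled total, since the Analysis Plan now tests hydromorphone unscaled. Keep the scaled versions and the planned hydromorphone comparison as supportive.
- Report ketamine and PCA use by arm, because an opioid total does not capture ketamine.

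The analgesic regimen does not change.

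**Cost.** The postoperative data are already collected, so the work is wording and one table. Conversion factors are approximate; under case (a), an oxycodone factor wrong by two either way still left total-opioid power at 0.72 to 0.78. Power could be somewhat lower if lidocaine does not affect oxycodone use. Neither the Table of Events nor Appendix A lists preoperative narcotic amounts, so putting those in the same unit could need extra chart data. The Safety Monitoring Plan reports a safety analysis of the first 15 patients, so the trial is under way and the change needs a dated amendment made blind to outcome by arm.

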Appendix A.

DATA COLLECTION POINTS

Age
Race
Sex
Height
Weight
BMI
Date of Injury/Wound
Mechanism of Injury/Wound
TBSA % Burned /Size of wound
Medical History
Physical Exam
Randomization
OR Procedure
OR Date
OR Incision Time
OR Extubation Time
OR Medication Data Collection
Donor Site Dimensions
Lidocaine levels at 60 minutes and 6 hours post op
Time of Study Treatment Soak Placement
Additional Epinephrine Soak Required
Time of Study Treatment Spray Placement
Time of Therabond Placement

Time of PACU/BICU Admission (Post-operatively)

PACU/BICU Post –op Narcotic Medication

Documentation of Verbal Numerical Rating Scale Pain Assessment (Time): 30 minutes after extubation, 2 hours, 6 hours and 24 hours post op obtained by research staff for both donor site and overall pain

Self- Reported Pain Assessment (Time): Collect from EPIC for first 24 hours

Wound Healing Assessment (14-21 days post op[+/-5days]) Performed per standard of care

Photographs (OR and 14-21 days post op[+/-5days])

Adverse/SA Event Assessment

Overall Narcotic Medication Data Collection from EPIC (0-72 hours post op)

[figure not shown]
Date of new onset infection of donor site

Antibiotics for donor site infection

APPENDIX B.

Verbal Numeric Pain Rating Scale

0–10 Numeric Pain Rating Scale

Appendix C.

Case Report Forms

Patient Initials: _____

Page 1 of 1

Patient ID: _____

_____-_____-_____
Date

Inclusion/Exclusion Criteria

Inclusion Criteria (all must be checked Y)

Y N

		Is the subject 18 years of age or older?
		Has the subject suffered second to third degree burns or a wound requiring a single splitthickness skin graft surgery?
		Are donor sites to be harvested estimated to be between 1-15%TBSA?
		Is the subject willing and able to give informed consent?
		ICF Date: _____-_____ -_____
		The subject is not participating in another interventional clinical trial?

Exclusion Criteria (all must be checked N)

Y	N	N/A	
			Is the subject pregnant? Pregnancy Test Type: _____ Pregnancy Test Date: ____-____-____
			Does the subject have a history of major renal or liver dysfunction?
			Does the subject have a history of seizures or major neurologic deficiencies?
			Does the subject have allergies to local anesthetics or hydromorphone? 
			Does the subject have any other injuries that could significantly contribute to pain? (ex: multi-trauma patient)

Eligibility Exceptions:

Patient Initials: _____

Page 1 of 2

Patient ID: _____-_____

_____ - _____
Date

Baseline

Demographics:

Date of Burn Injury: ____ / ____ / ____

Date of Admission: ____ / ____ / ____

Age: ____

Sex: M F

Race: Caucasian
 African American
 Asian

Height: ____ in. Weight: ____ kgs. BMI: ____

Hispanic

Other: _____

Mechanism of Injury:

Flame

Scald

Chemical

Electrical

Contact

Other (Non-Burn)

TBSA % Total: ____ % or not applicable

TBSA % Partial Thickness: ____ % or not applicable

TBSA % Full Thickness: _____% or [] not applicable

Illnesses/Past Medical History:

[] None	[] Cancer	[] COPD
[] CV Disease	[] Diabetes	[] ETOH
[] Hypertension	[] Renal Disease	[] Substance Abuse
[] Seizure Disorder	[] Stroke	[] Other: Specify _____

Comments:

Patient Initials: _____

Page 2 of 2

Patient ID: _____ - _____

____ - ____ - ____
Date

Baseline

Physical Exam:

Vitals:			
System	Abnormal	Normal	Explanation
General			
HEENT			
Cardiovascular			
Respiratory			
Gastrointestinal			
Genitourinary			
Musculoskeletal			

Skin			
Neurologic			
Psychiatric			
Endocrine			
Heme/Lymphatic			
Allergic/Immunologic			

Patient Initials: ____-____

Page 1 of 1

Patient ID: ____-____

____-____-____
Date

Randomization

Date Randomized: ____-____-____

Time Randomized*: ____:____

Order placed in EPIC to Randomize/Dispense Study Medication:

Date: ____ / ____ / ____ Time: _____

Randomization Materials to be stored in Investigational Drug Pharmacy until study completion.

*Time dispensed on study drug/placebo packaging

Comments:

Patient Initials: ____-____**Page 1 of 1****Patient ID:** ____-____**____-____-____****Date****Surgical Procedure****Surgical Procedure Information:**

OR Date: ____ / ____ / ____ Incision Time: ____ : ____ Extubation Time: ____ :

Procedure Performed:

Area of Donor Site Harvest*: [] Left Thigh
[] Right Thigh
[] Other: _____

Donor Site Harvest Time: _____

Donor Site Dimensions: ____ cm x ____ cm = ____ cm²

Photos of Donor Sites Complete: [] Yes [] No

Time of Study Treatment Soaks:

Time ON ____ : ____ Time OFF ____ : ____

Time ON ____ : ____ Time OFF ____ : ____

Need for additional Epinephrine Soaks: [] Yes [] No

Time ON ____ : ____ Time OFF ____ : ____

Time of Study Spray Treatment: ____ : ____

Time of TheraBond Placement: ____ : ____

Post Op Admit to: [] BICU [] PACU

Post Op Admit Time: ____ : ____

* One page to be completed per donor site

Patient Initials: ____-____

Page 1 of 4

Patient ID: ____-____

____-____
Date

Post-OP Study Assessments- 30 Minutes Post Extubation

30 Minute Post-extubation VNRS Pain Assessment:

Is the subject able to provide VNRS Pain Assessment related to donor site pain only:

[] Yes [] No

Time: ____ : ____ Score : ____

Is the subject able to provide VNRS Pain Assessment related to overall pain:

[] Yes [] No

Time: ____ : ____ Score : ____

VNRS Pain Assessment recorded by: _____

Comment: [] Yes [] No

Post-OP Study Assessments- 60 Minutes (+/- 30 minutes)

60 Minute Post-op Lidocaine Level:

Lidocaine Level Drawn By: [] Shands Lab Phlebotomy [] Research Staff

Time of Lab Draw: ____ : ____ Result: ____ mcg/mL **Normal Range 1.5-5.0 mcg/mL**

Lidocaine Level added to Participant Tracking Log: [] Yes [] No

Comment: Yes No

Patient Initials: _____

Page 2 of 4

Patient ID: _____ - _____

_____ - _____
Date

Post-OP Study Assessments- 2 Hours

2 Hour Post-op VNRS Pain Assessment:

Is the subject able to provide VNRS Pain Assessment related to donor site pain only:

Yes No

Time: ____: ____ Score : _____

Is the subject able to provide VNRS Pain Assessment related to overall pain:

Yes No

Time: ____: ____ Score : _____

VNRS Pain Assessment recorded by: _____

Comment: Yes No

Post-OP Study Assessments- 6-Hours (+/-60 minutes)

6 Hour Post-op Lidocaine Level:

Lidocaine Level Drawn By: Shands Lab Phlebotomy Research Staff

Time of Lab Draw: ____:____ Result: _____ mcg/mL **Normal Range 1.5-5.0 mcg/mL**

Lidocaine Level added to Participant Tracking Log: Yes No

Comment: Yes No

For more information, contact the Office of the Vice President for Research and Economic Development at [contact] or [contact].

Patient Initials:

Page 3 of 4

Patient ID: -

Post-OP Study Assessments- 6 Hours

6 Hour Post-op VNRS Pain Assessment:

Is the subject able to provide VNRS Pain Assessment related to donor site pain only:

[] Yes [] No

Time: ____ : ____ Score : _____

Is the subject able to provide VNRS Pain Assessment related to overall pain:

[] Yes [] No

Time: ____ : ____ Score : _____

VNRS Pain Assessment recorded by: _____

Comment: Yes No

Comments:

Patient Initials:

Page 4 of 4

Patient ID: -

Date

Post-OP Study Assessments- 24-Hours

24 Hour Post-op VNRS Pain Assessment:

Is the subject able to provide VNRS Pain Assessment related to donor site pain only:

[] Yes [] No

Time: ____ : ____ Score : _____

Is the subject able to provide VNRS Pain Assessment related to overall pain:

[] Yes [] No

Time: ____ : ____ Score : _____

VNRS Pain Assessment recorded by: _____

Comment: Yes No

Comments:

Patient Initials:

Page 1 of 1

Patient ID: -

— · — · —

Date

Follow-Up Assessment- 14-21 Days Post-op (+/- 5 days)

Follow-Up Assessment:

Date of follow-up appointment: ____ / ____ / ____

Has there been any infections to the Study Donor Site area?

[] Yes [] No

Has the Therabond been completely removed from the Study Donor Site?

[] Yes [] No

Is the donor site 100% healed? [] Yes [] No : _____ % healed

Current Treatment for Study Donor Site: _____

Photographs taken of Study Donor Site? [] Yes [] No

Photographs taken of Study Donor Site? [] Yes

Comments:

Patient Initials:

Page 1 of ____

Patient ID: ____-____ **ADVERSE EVENTS**

Adverse Event # ____

AE Start Date: ____ / ____ / ____

AE Stop Date: ____ / ____ / ____

AE Resolved: Yes No

AE Type: AE SAE

AE Description: _____

Is this event listed on the consent form? Yes No

Severity:	 Mild- Grade1	Relationship:	 Not Related
	 Moderate – Grade 2		 Possibly Related
	 Severe – Grade 3		 Probably Related
	 Life Threatening – Grade 4		 Related
	 Fatal - Grade 5		

Actions Taken:	 None	Clinical Outcomes:	 Death
	 Medication Administered		 Recovered Baseline
	 Additional Treatment		 Recovered w sequelae
	 Withdrawn from Study		 Symptoms Continue
	 Other		

Burn Sub-I Signature: _____

Investigator Signature: _____

Patient Initials: _____ **Page 1 of 1**

Patient ID: ____-____

All medication data information will be collected and entered into an excel spreadsheet.
